**Infusion-Related Reactions**

Severity Grade of the Event (NCI CTCAE version 4.03)	Dose Modifications	Toxicity Management
Any Grade	General Guidance	
For Any Grade:
 
 
– Manage per institutional standard at the discretion of investigator.
 
– Monitor patients for signs and symptoms of infusion-related reactions (e.g., fever and/or shaking chills, flushing and/or itching, alterations in heart rate and blood pressure, dyspnea or chest discomfort, or skin rashes) and anaphylaxis (e.g., generalized urticaria, angioedema, wheezing, hypotension, or tachycardia).
 

Grade 1 or 2	
For Grade 1:
 
The infusion rate of study drug/study regimen may be decreased by 50% or temporarily interrupted until resolution of the event.
 
For Grade 2:
 
The infusion rate of study drug/study regimen may be decreased 50% or temporarily interrupted until resolution of the event.
 
Subsequent infusions may be given at 50% of the initial infusion rate.
	
For Grade 1 or 2:
 
 
– Acetaminophen and/or antihistamines may be administered per institutional standard at the discretion of the investigator.
 
– Consider premedication per institutional standard prior to subsequent doses.
 
– Steroids should not be used for routine premedication of Grade <math>\leq 2</math> infusion reactions.
 

Grade 3 or 4	
For Grade 3 or 4:
 
Permanently discontinue study drug/study regimen.
	
For Grade 3 or 4:
 
 
– Manage severe infusion-related reactions per institutional standards (e.g., IM epinephrine, followed by IV diphenhydramine and ranitidine, and IV glucocorticoid).
 

CTCAE Common Terminology Criteria for Adverse Events; IM intramuscular; IV intravenous; NCI National Cancer Institute.

**Non-Immune-Mediated Reactions**

Severity Grade of the Event (NCI CTCAE version 4.03)	Dose Modifications	Toxicity Management
Any Grade	Note: Dose modifications are not required for AEs not deemed to be related to study treatment (i.e., events due to underlying disease) or for laboratory abnormalities not deemed to be clinically significant.	Treat accordingly, as per institutional standard.
Grade 1	No dose modifications.	Treat accordingly, as per institutional standard.
Grade 2	Hold study drug/study regimen until resolution to $\leq$ Grade 1 or baseline.	Treat accordingly, as per institutional standard.
Grade 3	Hold study drug/study regimen until resolution to $\leq$ Grade 1 or baseline.  For AEs that downgrade to $\leq$ Grade 2 within 7 days or resolve to $\leq$ Grade 1 or baseline within 14 days, resume study drug/study regimen administration. Otherwise, discontinue study drug/study regimen.	Treat accordingly, as per institutional standard.
Grade 4	Discontinue study drug/study regimen (Note: For Grade 4 labs, decision to discontinue should be based on accompanying clinical signs/symptoms, the Investigator's clinical judgment, and consultation with the Sponsor.).	Treat accordingly, as per institutional standard.

Note: As applicable, for early phase studies, the following sentence may be added: "Any event greater than or equal to Grade 2, please discuss with Study Physician."  
 AE Adverse event; CTCAE Common Terminology Criteria for Adverse Events; NCI National Cancer Institute.

NU Study Number: NU 15B01

Other Study Number: MedImmune # ESR-14-10694 (D4190C00030)

**4.4 Concomitant Medications/Treatments**

The investigator must be informed as soon as possible about any medication taken from the time of screening until the end of the clinical phase of the study (final study visit). Any concomitant medication(s), including herbal preparations, taken during the study will be recorded in the appropriate eCRF. Restricted, prohibited, and permitted concomitant medications are described in the following tables. Refer to Table 2 for guidance on management of IP-related toxicities.

**Prohibited concomitant medications**

Prohibited medication/class of drug:	Usage:
Any investigational anticancer therapy other than those under investigation in this study	Should not be given concomitantly whilst the patient is on study treatment
mAbs against CTLA-4, PD-1, or PD-L1 other than those under investigation in this study	Should not be given concomitantly whilst the patient is on study treatment
Any concurrent chemotherapy, radiotherapy, immunotherapy, or biologic or hormonal therapy for cancer treatment other than those under investigation in this study	Should not be given concomitantly whilst the patient is on study treatment. (Concurrent use of hormones for non-cancer-related conditions [eg, insulin for diabetes and hormone replacement therapy] is acceptable. Local treatment of isolated lesions, excluding target lesions, for palliative intent is acceptable [eg, by local surgery or radiotherapy])
Immunosuppressive medications including, but not limited to, systemic corticosteroids at doses exceeding 10 mg/day of prednisone or equivalent, methotrexate, azathioprine, and tumor necrosis factor- $\alpha$ blockers	
Should not be given concomitantly, or used for premedication prior to the I-O infusions. The following are allowed exceptions:
 
 
• Use of immunosuppressive medications for the management of IP-related AEs,
 
• short-term premedication for patients receiving combination agent where the prescribing information for the agent requires the use of steroids for documented hypersensitivity reactions
 
• Use in patients with contrast allergies.
 
• In addition, use of inhaled, topical, and intranasal corticosteroids is permitted.
 
 
A temporary period of steroids will be allowed if clinically indicated and considered to be essential for the management of the patient (eg, chronic obstructive pulmonary disease, radiation, nausea, etc).

Drugs with laxative properties and herbal or natural remedies for constipation	Should be used with caution through to 90 days after the last dose of tremelimumab during the study
Sunitinib	Should not be given concomitantly or through 90 days after the last dose of tremelimumab (acute renal failure has been reported with combination therapy of tremelimumab and sunitinib)
EGFR TKIs	Should not be given concomitantly. Should be used with caution in the 90 days post last dose of durvalumab. Increased incidences of pneumonitis (with third generation EGFR TKIs) and increased incidence of transaminase increases (with 1 st generation EGFR TKIs) has been reported when durvalumab has been given concomitantly.
Live attenuated vaccines	Should not be given through 30 days after the last dose of IP (including SoC)

**NU Study Number: NU 15B01**  
**Other Study Number: MedImmune # ESR-14-10694 (D4190C00030)**  
**Rescue Medications**

Rescue/supportive medication/class of drug:	Usage:
Concomitant medications or treatments (eg, acetaminophen or diphenhydramine) deemed necessary by the Investigator to provide adequate prophylactic or supportive care, except for those medications identified as "prohibited" as listed above	To be administered as prescribed by the Investigator
Best supportive care (including antibiotics, nutritional support, growth factor support, correction of metabolic disorders, optimal symptom control, and pain management [including palliative radiotherapy, etc])	Should be used when necessary for all patients

#### **4.5 Other Restrictions During the Study**

##### **4.5.1 Birth control**

The following restrictions apply while the patient is receiving study treatment and for the specified times before and after:

Female patient of child-bearing potential

- Females of childbearing potential who are sexually active with a non-sterilized male partner must use at least 1 **highly** effective method of contraception (Table 1) from the time of screening and must agree to continue using such precautions for 180 days after the last dose of durvalumab + tremelimumab combination therapy or 90 days after the last dose of durvalumab monotherapy. Non-sterilized male partners of a female patient must use male condom plus spermicide throughout this period. Cessation of birth control after this point should be discussed with a responsible physician. Not engaging in sexual activity for the total duration of the drug treatment and the drug washout period is an acceptable practice; however, periodic abstinence, the rhythm method, and the withdrawal method are not acceptable methods of birth control. Female patients should also refrain from breastfeeding throughout this period.

Male patients with a female partner of childbearing potential

- Non-sterilized males who are sexually active with a female partner of childbearing potential must use a male condom plus spermicide from screening through 180 days after receipt of the final dose of durvalumab + tremelimumab combination therapy or 90 days after receipt of the final dose of durvalumab monotherapy. Not engaging in sexual activity is an acceptable practice; however, occasional abstinence, the rhythm method, and the withdrawal method are not acceptable methods of contraception. Male patients should refrain from sperm donation throughout this period.
- Female partners (of childbearing potential) of male patients must also use a highly effective method of contraception throughout this period (Table 1).

N.B Females of childbearing potential are defined as those who are not surgically sterile (ie, bilateral tubal ligation, bilateral oophorectomy, or complete hysterectomy) or post-menopausal.

Women will be considered post-menopausal if they have been amenorrheic for 12 months without an alternative medical cause. The following age-specific requirements apply:

- Women <50 years of age would be considered post-menopausal if they have been amenorrheic for 12 months or more following cessation of exogenous hormonal treatments and if they have luteinizing hormone and follicle-stimulating hormone levels in the post-menopausal range for the institution or underwent surgical sterilization (bilateral oophorectomy or hysterectomy).
- Women ≥50 years of age would be considered post-menopausal if they have been amenorrheic for 12 months or more following cessation of all exogenous hormonal treatments, had radiation-induced menopause with last menses >1 year ago, had chemotherapy-induced menopause with last menses >1 year

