- Women  $\geq 50$  years of age would be considered post-menopausal if they have been amenorrheic for 12 months or more following cessation of all exogenous hormonal treatments, had radiation-induced menopause with last menses  $>1$  year ago, had chemotherapy-induced menopause with last menses  $>1$  year ago, or underwent surgical sterilization (bilateral oophorectomy, bilateral salpingectomy or hysterectomy).

3.1.13 Female and male patients of reproductive potential must agree to use effective birth control from screening to 180 days after the last dose of durvalumab + tremelimumab combination therapy or 180 days after the last dose of durvalumab monotherapy, whichever is the longer time period.[Refer Section 4.5.1]

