**NU Study Number: NU 15B01**

**Other Study Number: MedImmune # ESR-14-10694 (D4190C00030)**

Should a female patient become pregnant or suspect she is pregnant while participating in this study, she should inform her treating physician immediately. Refer to section 4.5.1 for details.

- 3.1.14 Willingness to provide a fresh biopsy prior to study enrollment and after 2 cycles of treatment as clinically appropriate per PI discretion
- 3.1.15 Patients must have the ability to understand and the willingness to sign a written informed consent prior to registration on study. Written informed consent and HIPAA authorization will be obtained from the subject prior to performing any protocol-related procedures, including screening evaluations
- 3.1.16 Subject is willing and able to comply with the protocol for the duration of the study including undergoing treatment and scheduled visits and examinations including follow up.

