#### **Paternal exposure**

Male patients should refrain from fathering a child or donating sperm during the study and for 180 days after the last dose of durvalumab + tremelimumab combination therapy or 90 days after the last dose of durvalumab monotherapy, whichever is the longer time period.

Pregnancy of the patient's partner is not considered to be an AE. However, the outcome of all pregnancies (spontaneous miscarriage, elective termination, ectopic pregnancy, normal birth, or congenital abnormality) occurring from 180 days after the last dose of durvalumab + tremelimumab combination therapy or 90 days after the last dose of durvalumab monotherapy, whichever is the longer time period if possible, be followed up and documented.

Where a report of pregnancy is received, prior to obtaining information about the pregnancy, the Investigator must obtain the consent of the patient's partner. Therefore, the local study team should adopt the generic ICF template in line with local procedures and submit it to the relevant Ethics Committees (ECs)/Institutional Review Boards (IRBs) prior to use.

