## **APPENDIX A- EFFECTIVE METHODS OF CONTRACEPTION**

Please refer to section 4.5.1 for details

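### The contraception period after durvalumab monotherapy is 180 days in inclusion criterion 3.1.13 but 90 days in Section 4.5.1, the section that criterion refers to

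*Combined protocol and SAP*

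**What the plan says.** Four places in the current protocol bear on how long contraception continues.

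- **Section 3.1, criterion 3.1.13** (female and male patients). Birth control starts at screening. It continues for 180 days after the last combination dose or "180 days after the last dose of durvalumab monotherapy, whichever is the longer time period". The criterion then refers to Section 4.5.1.
- **Section 4.5.1, Birth control.** Female patients continue for "180 days after the last dose of durvalumab + tremelimumab combination therapy" or "90 days after the last dose of durvalumab monotherapy". Male patients have the same 180 days after combination therapy, or "90 days after receipt of the final dose of durvalumab monotherapy". Neither sentence has a longer-of clause. Breastfeeding, sperm donation and partner contraception are tied to the same period.
- **Section 7.2.6.2, Paternal exposure.** Fathering a child, sperm donation and the documentation of partner pregnancies are tied to 180 days after combination therapy or "90 days after the last dose of durvalumab monotherapy, whichever is the longer time period".
- **Appendix A** gives no duration: "Please refer to section 4.5.1 for details". The pregnancy paragraph under 3.1.13 does the same: "Refer to section 4.5.1 for details".

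**The concern.** A reader who follows the cross-reference in 3.1.13 arrives at a different rule. The criterion states what a patient must agree to at entry. Section 4.5.1 is the restriction that applies on study. Staff working from 4.5.1 would release a patient from the obligation earlier than 3.1.13 requires. Appendix A and the pregnancy paragraph lead only to 4.5.1, so no other section settles the matter.

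The missing longer-of clause in 4.5.1 is a second problem. Every patient on maintenance has normally had combination therapy as well, so both periods in 4.5.1 apply to that patient, and the section does not say which one ends the obligation.

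The conflict also arises at retreatment. Section 4.1.2 requires criteria 3.1.11 to 3.1.15 to be met again, as applicable, before further durvalumab.

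**Working it through.** This is a consistency check of the text. No sample size, power or error rate is involved, and the plan gives no figure to reproduce. Date arithmetic is used only to size the gap.

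**Inputs**
- Last combination dose: four doses every 4 weeks from the start of treatment (Section 4.1), so Week 12, or 12 × 7 = day 84 after the first dose.
- Maintenance: every 2 weeks from Week 16, up to 18 doses (Section 8.3). Dose k falls on day 112 + 14 × (k − 1).
- Last maintenance dose if all 18 are given: Week 16 + 17 × 2 = Week 50, day 350.
- Periods: 180 days after both phases (3.1.13); 180 days after combination and 90 days after monotherapy (4.5.1).

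**Formulas**, with M the day of the last maintenance dose
- End under 3.1.13: max(84 + 180, M + 180) = M + 180 for any patient on maintenance.
- End under 4.5.1, reading A (the monotherapy period governs once maintenance has begun): M + 90.
- End under 4.5.1, reading B (the longer of its two periods governs): max(264, M + 90).

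| Maintenance doses | M (day) | 3.1.13 ends | 4.5.1 ends, reading A | Gap A | 4.5.1 ends, reading B | Gap B |
|---|---|---|---|---|---|---|
| 1 | 112 | 292 | 202 | 90 | 264 | 28 |
| 2 | 126 | 306 | 216 | 90 | 264 | 42 |
| 5 | 168 | 348 | 258 | 90 | 264 | 84 |
| 6 | 182 | 362 | 272 | 90 | 272 | 90 |
| 18 | 350 | 530 | 440 | 90 | 440 | 90 |

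Under reading B the monotherapy period overtakes the combination period when M + 90 > 264, that is M > 174. The first such dose is the sixth (day 182, Week 26).

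In weeks, for the full course: 50 + 90/7 = 62.9 under 4.5.1 and 50 + 180/7 = 75.7 under 3.1.13.

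A patient who stops after one maintenance dose therefore has three possible end dates: day 202, day 264 or day 292. A patient who stops during the combination phase has no conflict, because both sections give 180 days.

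**The case against.** The strongest reply is that the two rules can be met together: a patient who observes the longer period satisfies both sections. Section 4.5.1 also asks that stopping birth control be discussed with a responsible physician. Both points are true and reduce the practical risk. They do not tell staff when the obligation ends, and a physician consulting 4.5.1 would find 90 days.

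Several stronger readings are tempting, and the documents do not support them.

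- **A flat 90-day gap for every patient.** This needs reading A. Section 7.2.6.2 has a longer-of clause, so reading B of 4.5.1 is reasonable, and under it the gap is smaller up to the fifth maintenance dose.
- **3.1.13 refers to 7.2.6.2 as well.** It refers only to 4.5.1. Section 7.2.6.2 repeats the 90 days independently.
- **Follow-up of pregnancies in female patients is contradictory.** Criterion 3.1.13 sets a contraception period and no follow-up period. The maternal part of 7.2.6.2 has no 90- or 180-day window. The 90-day figure there concerns male patients and their partners.
- **Patients are told two end dates, or fetal harm follows.** The consent pages are not available for review, and no washout figure for days 90 to 180 is used here. Neither claim can be tested.
- **The change log shows which figure is right.** Appendix E records that Amendment 4 moved the inclusion criterion from 90 to 180 days, which may explain the mismatch. It also records a later revision of 4.5.1 in Amendment 8. The log does not settle the question, and the contradiction stands on the current text without it.

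Appendix E also states that the study closed on 7.20.2020 for low accrual, before the current version date. The number of patients whom a correction would still reach is therefore limited, and the documents do not give it.

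**Conclusion.** The contradiction is real and lies between operative sections of the current protocol. Criterion 3.1.13 and Section 4.5.1 give different contraception periods after durvalumab monotherapy, and 4.5.1 does not say how its two periods combine.

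It affects patients of reproductive potential who reach maintenance, and under either reading the gap is never zero for them. It is 90 days throughout under reading A. Under reading B it runs from 28 days after one maintenance dose to 90 days from the sixth on. These figures assume dosing on schedule, with the last combination dose at Week 12 and maintenance from Week 16. Delays would move the dates.

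This is an inconsistency in a patient-safety rule and should be corrected. It has no bearing on response rate, PFS, OS, sample size or any planned analysis. Nothing here judges which duration is appropriate.

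**What to change.** Reconcile criterion 3.1.13, Section 4.5.1 and Section 7.2.6.2 so that two things read the same in all three: the contraception period after durvalumab monotherapy, and the rule for a patient who received both phases. The sponsor decides what that period and rule are.

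In the same edit, check two related windows against the result: the one for partner pregnancies in Section 7.2.6.2, and the one in Section 7.2.4 for patients to report a pregnancy, which is 30 days or five half-lives after the treatment period, whichever is longer.

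The cost is an amendment to protocol wording, plus a check that the consent form agrees with it. No new data collection and no change to the analysis are needed.

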**NU Study Number: NU 15B01**

**Other Study Number:** MedImmune # *ESR-14-10694 (D4190C00030)*  
 ago, or underwent surgical sterilization (bilateral oophorectomy, bilateral salpingectomy or hysterectomy).

Highly effective methods of contraception, defined as one that results in a low failure rate (ie, less than 1% per year) when used consistently and correctly are described in Table 1. Note that some contraception methods are not considered highly effective (eg. male or female condom with or without spermicide; female cap, diaphragm, or sponge with or without spermicide; non-copper containing intrauterine device; progestogen-only oral hormonal contraceptive pills where inhibition of ovulation is not the primary mode of action [excluding Cerazette/desogestrel which is considered highly effective]; and triphasic combined oral contraceptive pills).

**Table 1. Highly effective methods of contraception (<1% failure rate)**

Barrier/Intrauterine methods	Hormonal Methods

 
• Copper T intrauterine device
 
• Levonorgestrel-releasing intrauterine system (eg, Mirena®)a
 
	
 
• Etonogestrel implants: eg, Implanon or Norplan
 
• Intravaginal device: eg, ethinylestradiol and etonogestrel
 
• Medroxyprogesterone injection: eg, Depo-Provera
 
• Normal and low dose combined oral contraceptive pill
 
• Norelgestromin/ethinylestradiol transdermal system
 
• Cerazette (desogestrel)
 

a This is also considered a hormonal method

#### 4.5.2 Blood donation

Subjects should not donate blood while participating in this study, or for at least 90 days following the last infusion of durvalumab or tremelimumab.

#### 4.6 Duration of Therapy

Patients may continue for 12 months of treatment or until any of the following occur:

- Disease progression
- Development of an inter-current illness that prevents further administration of treatment
- Unacceptable adverse event(s)
- Patient decides to withdraw from either study treatment or the as a whole study
- The treating investigator determines that the patient should be taken off treatment for any reason (i.e. changes in condition, inability to comply with study treatment or procedures)

#### 4.7 Duration of Follow Up

After patients come off treatment they will be followed up at 3, 6, 9, 12 months and then every 6 months for 3 years for survival and progression of disease.

#### 4.8 Removal of Subjects from Study Treatment and/or Study as a Whole

Patients can be taken off the study treatment and/or study as a whole at any time at their own request, or they may be withdrawn at the discretion of the investigator for safety, behavioral or administrative reasons. The reason(s) for discontinuation must be clearly documented on the appropriate eCRF. In general, patients who are permanently discontinued from receiving investigational product will be followed for disease progression, survival, and safety, including the collection of any protocol-specified blood specimens, unless consent is withdrawn or the subject is lost to follow-up or administered subsequent therapy (see below). Subjects who decline to return to the site for evaluations will be offered follow-up by phone every 3 months as an alternative.

Patients will be permanently discontinued from study treatment and will not receive any

